5.2. Other Baseline Characteristics

Other baseline characteristics include body weight (in kg), height (in cm), body mass index (BMI; in kg/m²), and ECOG status. BMI will be calculated by the formula:

$$\text{BMI (kg/m}^2\text{)} = \text{weight} / (\text{height}^2) \text{ (round to 1 decimal point).}$$

Other baseline characteristics will be summarized by treatment arms and overall using descriptive statistics for continuous variables and using number and percentage of subjects for categorical variables. The summary of demographic and baseline characteristics data will be provided for the Safety Analysis Set.

A by-subject listing of other baseline characteristics will be provided by subject ID number in ascending order for All Enrolled Analysis Set.

5.3. Medical History

Medical history will be collected at screening for disease-specific conditions including solid tumor malignancy status, and general conditions (i.e, conditions not specific to the disease being studied).

A by-subject listing of medical history will be provided by treatment arms and subject ID number in ascending order for All Enrolled Analysis Set.

5.4. Prior Anti-Cancer Therapy

The details of prior anti-cancer therapy will be listed by treatment arms and subject ID number in ascending order for All Enrolled Analysis Set.

5.5. Prior and On Study Radiotherapy

The details of all radiotherapy will also be listed by treatment arms and subject ID number in ascending order for All Enrolled Analysis Set.

5.6. Surgeries and Procedures

A by-subject listing of prior and on-study surgeries and procedures will be provided by treatment arms and subject ID number in ascending order for All Enrolled Analysis Set.

6. EFFICACY ANALYSIS

Efficacy parameters will be summarized and listed by treatment arms based on the ITT Analysis Set. The analyses will be conducted using the IRC assessments based on standard response criteria applying Cheson 2007.

6.1. Definition and Analysis of Efficacy Endpoints

6.1.1. Primary and Supportive Analysis for Primary Endpoint

For the primary efficacy analysis, ORR will be evaluated by treatment arms using the IRC assessments in the ITT Analysis Set. Subjects who do not have sufficient baseline or on-study tumor assessment to characterize response status will be counted as non-responders. Estimates and the corresponding 95% CIs based on the Clopper-Pearson exact method will be provided.

A by-subject listing of overall response will be provided by treatment arms and subject ID number in ascending order.

6.1.2. Analysis for Secondary Endpoints

The ORR by Week 24 and corresponding 95% CIs will be evaluated by treatment arm using the IRC assessments in the ITT Analysis Set.

The time-to-event efficacy endpoints including PFS, DOR, and OS will be analyzed using the Kaplan-Meier method in the ITT Set, and the analysis of DOR will include subjects who achieve a PR or CR. Analyses may also be performed for subgroups defined by potential predictors of response. The Kaplan-Meier plot will be provided for PFS and OS.

PFS and DOR Censoring rules:

- 1) Subjects who discontinued study prior to PD or death will be censored on the last tumor assessment date.
- 2) Subjects who missed ≥ 2 consecutive tumor assessments, and did not have a PD prior to missing ≥ 2 consecutive tumor assessments will be censored on the last tumor assessment date prior to missing ≥ 2 consecutive assessments.
- 3) Subjects who received new anti-cancer therapy will be censored on the last assessment date prior to receiving new anti-cancer therapy.
- 4) Subjects who are alive and do not have any on-study tumor assessments will be censored on the randomization date (applicable only for PFS)

OS censoring rules:

- 1) Subjects who do not have a recorded death date will be censored on the last known alive date.

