6.3. Assessments for Premature Discontinuation from Study

If a subject discontinues idelalisib (for example, as a result of an AE) every attempt should be made to keep the subject in the study and continue to perform the required study-related follow-up and procedures. If this is not possible or acceptable to the subject or investigator, the subject may be withdrawn from the study. It is recommended that the investigator consults with the medical monitor prior to removing the subject from study for any reason except subject withdrawal of consent.

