6.6. End of Study

EOS assessments will be completed once it has been determined that the subject will discontinue the study. The EOT and EOS visits may be performed on the same day if the subject will be discontinuing study treatment and discontinuing the study at the same time (eg, withdrawal of consent).

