6.7. Survival Follow-Up

Survival follow-up will be conducted at annual intervals (± 4 weeks) for 5 years, starting at the EOS visit. Information may be gathered during a routine clinic visit or other contact with the subject, or via telephone. Information gathered will include anti-tumor treatment, secondary malignancies, survival status, and death details if applicable.

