1.2.2. Secondary Endpoints

- DOR, defined as the interval from the first documentation of CR or PR to the earlier of the first documentation of disease progression by independent review committee (IRC or death from any cause
- ORR by Week 24, defined as the proportion of subjects who achieve a PR or CR by Week 24
- Overall safety profile of idelalisib, including the incidence of AEs and clinically significant laboratory abnormalities, severity, timing, and relationship to idelalisib of any AEs; SAEs; or AEs leading to interruption, reduction, or discontinuation of idelalisib Time to onset of AEs of interest (AEIs) defined as the interval from the start of idelalisib treatment to the first documentation of start of AEI
- PFS, defined as the interval from randomization to the earlier of the first documentation of disease progression by IRC or death from any cause
- OS, defined as the interval from randomization to death from any cause
- Idelalisib trough (predose) and peak (1.5-hour samples) plasma concentrations assessed by validated bioanalytical method

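### PFS/DOR censoring rule 1, as worded, censors subjects who left the study without progression and died soon after, against the plan's own event definition

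*SAP*

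**What the plan says.** - **Event definitions, SAP 1.2.2.** "PFS, defined as the interval from randomization to the earlier of the first documentation of disease progression by IRC or death from any cause". DOR likewise ends at "disease progression by independent review committee (IRC or death from any cause". Neither is limited to deaths on study.
- **Censoring rule 1, SAP 6.1.2 (PFS and DOR).** "Subjects who discontinued study prior to PD or death will be censored on the last tumor assessment date".
- **The other rules, SAP 6.1.2.** Rule 2 censors before a gap of two or more consecutive missed assessments. Rule 3 censors before new anti-cancer therapy. Rule 4 (PFS only) censors at randomization those without any on-study assessment, provided they are alive. For OS, every recorded death is an event.
- **What leaving the study means, protocol 6.6.** "EOS assessments will be completed once it has been determined that the subject will discontinue the study".
- **What is collected afterwards, protocol 6.7.** "Survival follow-up will be conducted at annual intervals (± 4 weeks) for 5 years, starting at the EOS visit". "Information gathered will include anti-tumor treatment, secondary malignancies, survival status, and death details if applicable".
- **How a subject may come to leave without progression, protocol 6.3.** After idelalisib is stopped, sites must try to keep the subject on study. "If this is not possible or acceptable to the subject or investigator, the subject may be withdrawn from the study".
- **Precedence, SAP 1.** Where the two documents differ on analysis methods, the SAP governs.

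**The concern.** Leaving the study does not end the recording of deaths; survival follow-up begins at that point. Rule 1 is nevertheless keyed to study discontinuation. A subject who leaves free of progression and then dies did discontinue before death, so the wording sends that subject to the last scan date, however short the interval.

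Two things are at stake. The first is consistency: a known death would be an event in the OS analysis and a censored observation in PFS, although the PFS definition includes it. The second is bias. Subjects who leave because of toxicity or decline are plausibly at higher risk of early death, so censoring them is unlikely to be independent of outcome. It would make PFS and DOR look longer.

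**Working it through.** **1. The plan's own figures.** The stated chance of 60 or more responders among 120 at a true ORR of 56% is P(X ≥ 60 | n = 120, p = 0.56) = 0.921, which agrees with 92%. It does not depend on PFS or DOR. No stated figure depends on rule 1, and the documents give no PFS median, withdrawal rate or post-withdrawal mortality.

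**2. The rules applied to each kind of leaver.**

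| Subject | Literal result for PFS | Due to rule 1 alone? |
|---|---|---|
| Left because of IRC progression | Event at progression | No |
| Died on study (death is a listed reason in protocol 3.5.2) | Event at death | No |
| Started new anti-cancer therapy, then died | Censored by rule 3 | No |
| Died after missing two or more consecutive scans | Censored by rule 2 | No |
| Left, death never recorded (for example consent withdrawn) | Censored; no death to count | No |
| Left without progression or new therapy, at least one on-study scan, death recorded, fewer than two scans missed | Censored at last scan | **Yes** |
| Left without any on-study scan, death recorded soon after | Rule 1: censored, with no on-study scan date to use. Rule 4: not censored, because not alive | Rules 1 and 4 conflict |

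**3. A timeline on the current scan calendar (Weeks 12, 24, 36, 48, 60, 84).** A subject stops idelalisib at Week 10, is scanned without progression at Week 12, leaves the study at Week 13 and dies at Week 17. The next scan was due at Week 24, so none was missed, and no new therapy was given. Rules 2 and 3 do not apply. OS has an event at Week 17; PFS under rule 1 is censored at Week 12.

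**4. Illustrative size; every input is assumed.** Time to progression is exponential with median 48 weeks and is detected at the scheduled scans. A stated share of subjects is given a departure time uniform over Weeks 4 to 40. A stated fraction of those who leave without detected progression die 1 to 12 weeks later. Subjects whose progression is detected first remain events, so 20% × 120 × 50% = 12 deaths falls to 9.7. Kaplan-Meier PFS at Week 48:

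| Given a departure time | Of leavers, die | Rule 1 | Deaths counted | Difference (points) | Deaths dropped per 120 |
|---|---|---|---|---|---|
| 5% | 10% | | | about 0.2 | 0.5 |
| 10% | 10% | | | about 0.5 | |
| 15% | 10% | | | about 0.8 | 1.4 |
| 5% | 25% | 49.8% | 49.2% | 0.6 | 1.2 |
| 5% | 50% | 49.7% | 48.5% | 1.2 | |
| 10% | 50% | 50.0% | 47.4% | 2.6 | |
| 15% | 50% | 50.3% | 46.5% | 3.8 | |
| 20% | 50% | 49.7% | 44.4% | 5.3 | 9.7 |

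No counted death followed more than one missed scan, so the difference comes from rule 1 and not rule 2.

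**5. A second model for direction.** Assume exponential PFS with median 11 months, so 12-month PFS is 0.5^(12/11) = 0.469. A share of the PFS events are deaths within one 12-week scan interval of the last scan, after departure. Simulated 12-month PFS, deaths counted against rule 1: 47.0% v 48.6% (5% share), 47.0% v 50.4% (10%) and 46.5% v 51.6% (15%). The median rises from about 11 months to 11.5, 12.1 and 12.5 months. The direction is the same.

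**The case against.** - **Rule 1 may mean less than it says.** It can be read as leaving with neither progression nor death on record. Rule 4 and the endpoint definitions favour that intent. This stands, and it means one cannot say that the reported PFS and DOR will be overstated; that depends on how the rule is programmed. It does not rescue the wording, because the literal reading yields a different event count.
- **A reader might infer that everyone who leaves and later dies is lost to PFS.** The documents do not support that. Prior IRC progression and on-study death remain events, rules 2 and 3 already remove other cases, and unrecorded deaths cannot be counted under any rule. Stopping idelalisib does not trigger rule 1 either: such subjects are meant to stay on study for scans until progression, so the timeline above is an exception, though protocol 6.3 allows it.
- **The size is driven by assumptions.** This stands. Nothing in the documents sets a lower limit on mortality after departure; at 10% mortality the effect is under one point. Also, 120 per arm is the planned number, and SAP 1 reports early termination for slow enrollment.
- **A reader might infer that the rule flatters the more toxic arm and hides harm.** That is not shown. Neither calculation compares arms, and no arm-specific withdrawal rates are given. The deaths stay visible in the OS analysis and in the by-arm death summary (SAP 7.1.6.2), and Grade 4 or higher TEAEs are a primary endpoint. No formal testing is planned (SAP 3.5).

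**Conclusion.** Rule 1 is wrong as written, in a narrow form. Applied literally, it censors a recorded death that SAP 1.2.2 defines as a PFS or DOR event, and it conflicts with rule 4 for a subject who leaves unscanned and then dies. No look-back window or sensitivity analysis in the SAP repairs this.

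The affected group is leavers without IRC progression, without new anti-cancer therapy, and with a death captured before two scans were missed. The bias is upward. Its size cannot be computed from the documents; under the assumed rates above it runs from about 0.2 to 5.3 points of Week 48 PFS. PFS and DOR are secondary and descriptive, so no alpha, power or sample size is affected. The correction should be made, but it does not touch the primary endpoints.

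**What to change.** Replace rule 1 with:

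> Subjects with no IRC PD and no recorded death are censored on the last tumor assessment date. A death without prior IRC PD and before new anti-cancer therapy is an event on the date of death, whether or not the subject had left the study, unless two or more consecutive planned assessments fell between the last tumor assessment (or randomization if none) and death. Planned assessments are counted on the protocol scan calendar (Weeks 8/16/24 or 12/24, then 36, 48, 60, 84) as if it continued after study discontinuation, with a fixed pre-stated window after Week 84.

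The last sentence is needed. Survival follow-up includes no scheduled scans, and after Week 84 scans are at the investigator's discretion. Without a notional calendar and a window, a leaver never misses a planned assessment, and a death years later with unobserved progression could count as a PFS event.

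The cost is one SAP paragraph and one programming condition, using death dates already collected for OS. Reported PFS and DOR may be slightly lower. SAP 1 requires changes made after finalization to be documented in the CSR.

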Prior to Protocol Amendment 5, this study was originally designed to evaluate the safety and efficacy of administration of idelalisib in subjects with FL at either 150 mg twice daily (Arm A) or 100 mg twice daily (Arm B). Based on the 8-week response assessment, subjects randomized to 100 mg twice daily idelalisib with stable disease (SD) or progressive disease (PD) would dose escalate to 150 mg twice daily. Subjects randomized to 150 mg twice daily with SD would continue 150 mg twice daily idelalisib. Subjects randomized to 150 mg twice daily with PD were discontinued. The rationale for selecting an 8-week independent review committee (IRC) confirmed response assessment was based on data from Study 101-09 in which: 56% (40/71) of responses occurred at the first assessment by 2 months, 83% (59/71) occurred by 4 months, and 96% (67/71) occurred by 6 months.

The idelalisib safety profile in relapsed iNHL has observed Grade ≥ 3 transaminase elevations with a median time to onset of 1.6 months and minimal occurrence beyond 4 months. Pneumonitis may develop at any time during treatment (median time to onset of 4.8 months, range from 3.7 to 14.1 months). Grade ≥ 3 diarrhea/colitis has a median time to onset of 5 months and continues to occur throughout treatment at a rate of 0.041 per person years. Grade ≥ 3 rash has occurred at a median time to onset of 2 months, range from 0.4-7.9 months. These events are managed by dose interruptions, reductions, and re-escalation or discontinuation as medically appropriate.

As of Protocol Amendment 5, enrollment to Arm B was closed. This decision was based on preliminary data suggesting that Arm B appeared unlikely to meet Gilead's FDA PMR 2180-10 objective of achieving an overall response rate (ORR) $\geq 50\%$ and there would have been insufficient exposure to the 100 mg twice daily dosing regimen to evaluate intermediate and long-term safety.

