6.1.7. Radiology Assessment

Subjects will be imaged at neck, chest, abdomen, and pelvis with either PET-CT (diagnostic), contrast-enhanced CT, or gadolinium-enhanced MRI. If MRI is chosen, subjects will have an MRI of neck, abdomen, and pelvis, but will need a non-contrast enhanced CT of the chest. Chest x-ray, ultrasound, endoscopy, laparoscopy, radionuclide scans, or tumor markers will not be considered for response assessment. For radiographic evaluations, the same method of assessment and the same technique (eg, scan type, scanner, subject position, dose of contrast, injection/scan interval) should be used to characterize each identified and reported lesion at baseline and during study participation.

All relevant clinical and radiographic information required to make each assessment must be made available for source verification and for submission to the IRC.

Investigators will assess the status of each subject's disease using standard response criteria.

If disease progression is suspected, the IRC will be notified and radiographic images will be submitted to the IRC.

The IRC will review radiographic and pertinent clinical data in order to provide a definitive interpretation. The findings of the IRC will be considered primary for analyses of efficacy endpoints. It is recommended that the investigator consults with the medical monitor if considering removing a subject from study prior to a definitive IRC assessment of progression.

Radiographic assessments will be performed at the following visits:

Subjects enrolled as of Protocol Amendments 5 and 6:

Screening, Weeks 12, 24, 36, 48, 60, and 84 until IRC documented disease progression, and at EOT (unless radiographic assessments performed within 4 weeks prior to EOT visit). After Week 84, radiographic assessments are performed at the discretion of the investigator. Screening CT/PET-CT/MRI may be performed within 6 weeks prior to first dose. Subsequent scans may be done within 1 week prior to clinic visit.

Subjects enrolled prior to Protocol Amendment 5:

Screening, Weeks 8, 16, 24, 36, 48, 60, and 84 until IRC documented disease progression, and at EOT (unless radiographic assessments performed within 4 weeks prior to EOT visit). After Week 84, radiographic assessments are performed at the discretion of the investigator. Screening CT/PET-CT/MRI may be performed within 6 weeks prior to first dose. Subsequent scans may be done within 1 week prior to clinic visit.

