Responses will be categorized as complete response (CR), very good partial response, partial response (PR), stable disease (SD), or progressive disease (PD). In addition, a response category of not evaluable (NE) is provided for situations in which there is inadequate information to otherwise categorize response status. A response category of no disease (ND) is included for situations in which there is no evidence of tumor both at baseline and on-treatment.

The best overall response will be determined. The best overall response is the best response recorded from the start of study drug until PD/recurrence (taking as reference for PD the smallest measurements recorded since study drug started). Subjects with a best overall response of NE or ND will be included in the denominators in calculations of tumor response rate.

Response Categories

Complete Response

To satisfy criteria for CR, all of the following criteria must be met:

- No evidence of new disease
- Regression of all index nodal lesions to normal size (≤ 1.5 cm in the LD for nodes that were considered large at baseline and ≤ 1.0 cm in the LD and ≤ 1.0 cm in the LPD for nodes that were considered small at baseline) Regression to normal of all nodal non-index disease
- Disappearance of all detectable extra-nodal index and non-index disease
- Normal spleen and liver size by imaging studies, no hepatic or splenic lymphoma nodules, and no new liver or spleen enlargement
- Morphologically negative bone marrow based on an adequate unilateral core biopsy (> 20 mm unilateral core); if the sample is indeterminate by morphology, it should be negative by immunohistochemistry. After the subject meets radiographic CR, the window for bone marrow biopsy is within 30 days from the date that CR was met.
- If PET performed (not required), no evidence of residual disease

Partial Response

To satisfy criteria for PR, all of the following criteria must be met as noted below:

- No evidence of new disease
- A $\geq 50\%$ decrease from baseline in the SPD of the index lesions
- No increase in the size of non-index disease

- No increase in the size of the liver or spleen and no new liver or spleen enlargement
- Persistence of bone marrow involvement in a subject who meets other criteria for CR based on the disappearance of all nodal and extra-nodal masses
- If PET performed (not required):

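### The missed-scan censoring rule gives a negative duration of response for anyone whose first CR or PR comes after two missed scans

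*SAP*

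**What the plan says.** SAP section 6.1.2 puts PFS and DOR under a single list of four censoring rules. Rule 2 concerns subjects who missed at least two scans in a row with no PD beforehand: those who missed two or more "consecutive tumor assessments will be censored on the last tumor assessment date prior to missing" the run. The response date is not mentioned. Rule 4 in the same list is restricted to one endpoint: "Subjects who are alive and do not have any on-study tumor assessments will be censored on the randomization date (applicable only for PFS".

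The other relevant definitions are:

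- **Origin of DOR** (SAP 1.2.2): "DOR, defined as the interval from the first documentation of CR or PR to the earlier of the first documentation of disease progression" by the IRC, or death.
- **DOR population** (SAP 6.1.2): "the analysis of DOR will include subjects who achieve a PR or CR".
- **Who is a responder** (Protocol Appendix 6): "The best overall response is the best response recorded from the start of study drug until PD/recurrence". No condition on missed scans is attached.
- **Scan schedule** (Protocol 6.1.7): "Screening, Weeks 12, 24, 36, 48, 60, and 84 until IRC documented disease progression" for subjects enrolled as of Amendments 5 and 6, and "Screening, Weeks 8, 16, 24, 36, 48, 60, and 84 until IRC documented disease progression" for those enrolled earlier.

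**The concern.** For PFS the rule is coherent: time runs from randomization, so the last scan before a gap falls inside the interval. DOR starts later, at first response. If the gap comes before that response, the censoring date precedes the origin and the duration is negative.

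Such a subject is a responder for ORR and belongs in the DOR analysis. As the rule stands, the programmer must either leave the subject out, so that the DOR count falls short of the ORR responder count and the stated DOR population is not met, or choose a date that the SAP does not define. Two programmers could resolve it differently. SAP section 4.4 says COVID-19 disrupted the visit schedule, so missed scans are a realistic prospect.

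**Working it through.** The plan gives no figure for this point, so there is nothing to reproduce first. The check has three parts.

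**1. Date arithmetic.** DOR under rule 2 = date of the last scan before the gap − date of first CR/PR. Study days are from the Study Procedures Table (Protocol Appendix 2).

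| Schedule | Last scan before gap | Missed | First PR | DOR |
|---|---|---|---|---|
| As of Amendment 5 | Week 12, Day 85 (SD) | Weeks 24, 36 | Week 48, Day 337 | 85 − 337 = −252 days |
| Before Amendment 5 | Week 8, Day 57 (SD) | Weeks 16, 24 | Week 36, Day 253 | 57 − 253 = −196 days |

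**2. All gap patterns.** Listing every run of two or more missed scans followed directly by the first response, and taking the screening scan as Week 0 when no on-study scan precedes the gap:

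- As of Amendment 5: 10 patterns, all negative, the nearest to zero being −36 weeks. With an on-study scan before the gap the values run from −36 to −72 weeks.
- Before Amendment 5: 15 patterns, all negative, the nearest to zero being −24 weeks (Weeks 8 and 16 missed, response at Week 24). With an on-study scan before the gap they run from −28 to −76 weeks.
- If the first two scans are missed, the only prior assessment is the screening scan. It may be up to 6 weeks before first dose, so the value can be up to 6 weeks more negative.
- If the gap follows the response, the minimum is 0 on both schedules. The fault arises only when the gap comes first.

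**3. How often.** This needs assumptions. Scans are missed independently with probability q. Onset of response follows the prior single-arm study in Protocol 1.3: "56% (40/71) of responses occurred at the first assessment by 2 months, 83% (59/71) occurred by 4 months", and 67/71 by 6 months. The remaining 4 are assumed spread to Week 48. Onset is uniform within each interval, and response is held until documented. With one month taken as 4.348 weeks, the schedule as of Amendment 5 gives:

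- Onset by Week 12: 40/71 + (19/71) × (12 − 8.70)/8.70 = 0.665.
- Weeks 12–24: 0.252. Weeks 24–36: 0.053. Weeks 36–48: 0.031.

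The chance of at least two consecutive misses before the first documented response, at q = 10%, is q² = 1.00% if onset precedes the first scan and q²(2 − q) = 1.90% if it falls between the first and second. By enumeration it is 2.79% and 3.60% for the next two intervals. The weighted sum is 0.665 × 1.00 + 0.252 × 1.90 + 0.053 × 2.79 + 0.031 × 3.60 ≈ 1.40%.

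| Share of responders with negative DOR | q = 5% | q = 10% | q = 20% |
|---|---|---|---|
| As of Amendment 5 | 0.36% | 1.40% | 5.39% |
| Before Amendment 5 | 0.44% | 1.72% | 6.53% |
| As of Amendment 5, all onset by first scan | 0.25% | 1.0% | 4.0% |
| As of Amendment 5, onset uniform to Week 48 | 0.60% | 2.3% | 8.5% |
| As of Amendment 5, response may end before it is documented (simulation, 52-week median duration assumed) | 0.27% | 1.08% | 4.18% |

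The protocol prints 96% beside 67/71, which is 94.4%. Using 68/71 instead gives 0.35, 1.38 and 5.34% on the schedule as of Amendment 5.

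**Effect on the estimate.** In the same simulation (200,000 responders per rate), DOR at 36 weeks is 0.6297, 0.6326 and 0.6391 when only post-response gaps count, and 0.6296, 0.6321 and 0.6370 when the affected responders are dropped. The largest difference is 0.6391 − 0.6370 = 0.0021.

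**The case against.** DOR is defined from first response, and censoring rules govern follow-up after an endpoint's origin. A sensible programmer would therefore count only later scans. The PFS-only label on rule 4 is weak evidence of intent, because a responder always has an on-study assessment and rule 4 could never apply to DOR. Both points are fair, but the SAP does not state this reading, and no other rule in either document supplies it.

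The effect is also small and unproven. DOR is secondary and descriptive, no formal testing is planned, a Kaplan-Meier plot is promised only for PFS and OS, and the study stopped early. No affected subject is known. This stands, and it is why the point is minor.

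The percentages are soft. The miss rates are assumed, and the onset data come from a study of 125 iNHL subjects, only 72 with FL. Letting response end before documentation lowers the shares by about a quarter. Most counted cases also miss the first two scans: about 1.00/1.40 = 71% at q = 10% as of Amendment 5. For these the date falls back to the screening scan, unlike the two worked examples. On the earlier schedule, the Week 8 read drove unblinding and dose decisions, so independent misses there are doubtful. These limits affect the size, not the sign.

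Finally, after the fix PFS is still censored before the gap while DOR accrues from the later response, so the two endpoints treat the same follow-up differently. Rule 3 has a similar opening if a first response is recorded after new anti-cancer therapy. Both observations are correct, but neither makes the negative duration acceptable.

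**Conclusion.** The concern holds. Followed literally, rule 2 produces an impossible value for every responder whose first documented CR or PR comes after two or more consecutive missed scans. That conclusion rests on the text and the scan schedule alone and needs no assumed rate.

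Severity is minor. Under the stated assumptions the fault touches from a fraction of 1% to several percent of responders, depending mainly on the missed-scan rate. Dropping them changes the 36-week DOR estimate by about 0.002 at most when misses are independent. No headcount can be given, because the documents report no achieved enrollment or missed-scan rate. The primary endpoints are unaffected, and no effect on the PFS estimate is claimed. What suffers is the match between the DOR and ORR responder counts, and the reproducibility of the DOR analysis.

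**What to change.** Add to rule 2 in SAP section 6.1.2: *For DOR, only tumor assessments missed after the first documented CR or PR are considered.* In the Week 12 / Week 48 example, if Weeks 60 and 84 are attended without PD, DOR changes from −36 weeks to 84 − 48 = +36 weeks, censored at Week 84. The lowest value rule 2 can then give is 0. PFS is unchanged.

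The cost is one clause, with no new data and no extra analysis. The SAP is already signed, but its section 1 provides for later changes to be documented in the CSR, so the clause can be recorded there.
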